5.1 Sample Size Determination

With total sample size of 75 subjects, we have >80% power to detect an effect size for a change in HRSD (from week 0 to week 8) of at least (Cohen's) $d = 0.33$ (small-medium), using a 2-sided test with a 5% significance level. With this sample size we can construct 95% confidence intervals for the response/remission rates that are no more than 25 percentage points wide. For our subgroup analyses to examine the hypothesis that baseline pain (physical or emotional) will differentially relate to improvement in depression, assuming a median split (low/high, $n = 37/38$) for a given physical or emotional pain battery score, we have >80% power to detect an effect size for a difference in change in HRSD (low group vs. high group) of at least $d = 0.66$ (medium-large), using a 2-sided test with a 5% significance level. Similarly, we have >80% power to detect differences in proportions of responders/remitters between the pain groups that are at least 30 percentage points. As an example, if depression response/remission is 10% in the low pain group and 40% in the high pain group, we have 86% power to find this statistically significant at the 5% significance level.

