5.2 Statistical Methods

Descriptive analyses for all variables collected at all time points will be conducted both overall and by study site. If differences are found between the study sites on outcomes of interest, then study site will be adjusted for in the analyses. For the intent-to-treat sample (i.e. those who started on drug at week 1 regardless of compliance across the 8 weeks), we will report proportions of responders and remitters and mean changes in HRSD, VAS pain score, and ARSQ from week 0 to week 8. In addition to these point estimates, we will report the corresponding 95% confidence intervals. Similar analyses will be done on the sample of completers (i.e. those who complied with drug administration across all 8 weeks based on pill counts of at least 80%).

To examine the hypothesis that baseline pain level will be predictive of response to tianeptine, we will further investigate whether any single baseline pain battery score can be used to construct subgroups of subjects showing greater response to tianeptine. Based on the distribution of a given pain battery score and preliminary exploratory bivariate modelling, we will dichotomize the pain score (low/high) and compare response/remission rates and change scores for HRSD between the groups corresponding to low and high pain battery score. We will

report effect sizes corresponding to differences in response/remission rates and differences in HRSD change scores. Exploratory analyses will employ multivariable logistic (for response/remission outcomes) and linear (for HRSD change score) regression to investigate whether combinations of baseline pain scores can be used to identify subgroups who will show greater response to tianeptine. Additional analyses will employ multivariable logistic and linear regression to investigate associations between baseline neuropsychiatric and/or MRI measures and remission/response or HRSD change score. To take advantage of the fact that HRSD and TESS are collected at each study visit (8 post-baseline measures), we will also employ linear mixed effects models to investigate the effects of each baseline pain battery score on HRSD and TESS over time.

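### The claim of more than 80% power for any 30-point difference in response or remission fails at mid-scale rates, where power falls to about 75% (normal approximation) or 78% (exact chi-square)

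*Combined protocol and SAP*

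**What the plan says.** Section 5.1 (Sample Size Determination) opens "With total sample size of 75 subjects" and sets up the subgroup comparison "assuming a median split (low/high, $n = 37/38$) for a given physical or emotional pain battery score". For the HRSD change score it specifies power "using a 2-sided test with a 5% significance level". It then turns to the binary endpoints with the word Similarly and states that "we have >80% power to detect differences in proportions of responders/remitters between the pain groups that are at least 30 percentage points". One illustration follows: "if depression response/remission is 10% in the low pain group and 40% in the high pain group, we have 86% power".

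Section 5.2 (Statistical Methods) says the analysis will "compare response/remission rates and change scores for HRSD between the groups corresponding to low and high pain battery score". It names no test for the two-group comparison of rates. Neither Section 5.1 nor Section 5.2 restricts the rates to which the power statement applies. Section 4.1 lists response and remission as secondary endpoints and gives no expected values.

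**The concern.** The variance of a proportion is largest near 50%, so a fixed 30-point difference is harder to detect in the middle of the scale than near either end. A power statement for a difference in proportions therefore needs a base rate, or must be shown to hold at the least favourable one. Section 5.1 does neither. Its only example has a low rate of 10%, where power is comparatively high.

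The interval statement in the same section has the same any-rate form: "95% confidence intervals for the response/remission rates that are no more than 25 percentage points wide". That one does hold at every rate (checked below), so a reader has reason to take the power sentence as a worst-case bound too.

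What is at stake is how a null subgroup result is read. If the observed rates are mid-scale and the comparison is not significant, the stated power would overstate how firmly a 30-point difference had been ruled out.

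**Working it through.** **Inputs (all from Section 5.1).** Low-pain group n₁ = 37, high-pain group n₂ = 38, total 75; 5% significance level; difference 0.30. Two-sidedness is stated for the HRSD comparison and carried over by Similarly.

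**Formula (pooled normal approximation).**

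- p̄ = (37p₁ + 38p₂)/75
- SE₀ = √[p̄(1 − p̄)(1/37 + 1/38)]
- SE₁ = √[p₁(1 − p₁)/37 + p₂(1 − p₂)/38]
- Power = Φ[(0.30 − 1.96·SE₀)/SE₁]

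**Step 1: reproduce the plan's figure, 10% vs 40%.** p̄ = (3.7 + 15.2)/75 = 0.252; SE₀ = 0.1003; SE₁ = 0.0935; (0.30 − 1.96 × 0.1003)/0.0935 ≈ 1.106; power = **86.6%**, against the stated 86%. A one-sided test would give 92.6%, which does not match, so the two-sided reading is confirmed.

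**Step 2: same formula, mid-scale rates, 35% vs 65%.** p̄ = (12.95 + 24.7)/75 = 0.502; SE₀ = 0.1155; SE₁ = 0.1102; (0.30 − 1.96 × 0.1155)/0.1102 ≈ 0.669; power = **74.8%**.

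**Step 3: move the lower rate across the scale, difference fixed at 30 points.**

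| Rates | Power (pooled normal) |
|---|---|
| 5% vs 35% | 91.7% |
| 10% vs 40% | 86.6% |
| 18% vs 48% | 80.1% |
| 20% vs 50% | 78.9% |
| 25% vs 55% | 76.6% |
| 35% vs 65% | 74.8% (minimum) |
| 45% vs 75% | 76.7% |
| 50% vs 80% | 79.0% |
| 52% vs 82% | 80.2% |
| 55% vs 85% | 82.3% |

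In steps of 0.1 points, power is below 80% for lower rates from 18.2% to 51.7%. That is 33.5 of the 70 points the lower rate can span.

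**Step 4: does the choice of test matter?** Exact figures come from enumerating both binomial distributions.

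| Two-sided method | Minimum power | Lower rates giving less than 80% |
|---|---|---|
| Pooled normal approximation | 74.8% | 18.2–51.7% |
| Unpooled normal approximation | 77.7% | 24.1–46.3% |
| Arcsine approximation | 75.1% | 19.4–50.6% |
| Uncorrected Pearson chi-square, exact | 78.3% | 18.9–46.0% |
| Wald z, exact | 78.4% | 20.8–45.7% |
| Likelihood ratio, exact | 78.4% | 20.8–46.0% |
| Mid-p | 72.7% | 16.7–47.8% |
| Fisher's exact test | 70.9% | 13.9–53.4% |

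All eight fall below 80% for lower rates from 24.1% to 45.7%.

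**Step 5: what difference does have 80% power at every rate?** Worst case over base rates:

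- Pooled normal: 77.7% at 31 points, 80.4% at **32 points**.
- Exact Pearson: 78.3% at 30 points, 80.9% at **31 points**.
- Fisher: 79.6% at 33 points, 82.1% at **34 points**.

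By the pooled formula, 80% power at 35% vs 65% needs 43 per group, against 37 and 38 available.

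**Step 6: the neighbouring interval statement.** At n = 75 the widest Wald interval is 2 × 1.96 × √(0.25/75) = 22.6 points, and the widest Clopper–Pearson interval is 23.6 points. Both are under 25, so that sentence holds at every rate.

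**The case against.** No computed figure in the section is wrong. The only power value given with both rates reproduces, so the fault is a missing qualifier. The example that follows can be read as placing the claim at low rates, and up to a lower rate of about 18% the claim is true. The documents do not show that mid-scale rates are expected. The 74.8% is an approximation; the actual rejection probability of the uncorrected chi-square test never falls below 78.3%, only 1.7 points short. Finally, 37/38 is an assumed median split, while Section 5.2 lets the cut-point depend on the score distribution and exploratory modelling, so band limits to a tenth of a point have little practical meaning.

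Much of this stands as a limit on importance. It does not save the sentence. The example is offered as an illustration after a complete general claim, so it does not narrow that claim. The sentence covers both response and remission, and nothing in the plan confines both to the favourable range. More than 80% is a strict lower bound, and every two-sided method tried breaks it, including the unconditional exact tests of Boschloo (minimum 71.4%) and Barnard (71.8%). The chi-square figure is also slightly flattering, since that test's true size exceeds 5% at some rates (about 6.4%). On the cut-point, what follows is that the corrected sentence should use rounded limits and state the even split as an assumption.

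**Conclusion.** The concern holds. As written, the design does not have more than 80% power for every 30-point difference. The shortfall is at most 5.2 points by the formula that reproduces the plan's own example (80 − 74.8), 1.7 points for the exact chi-square test (80 − 78.3), and 9.1 points for Fisher's test (80 − 70.9). The 10% versus 40% example and the interval-width statement are both correct.

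Severity is minor: the sentence concerns a subgroup comparison on two secondary endpoints, and the sample size, primary analysis and all decisions are unaffected.

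The figures assume a two-sided 5% test, a 37/38 split and week-8 outcomes on all 75 subjects. Missing outcomes would lower power further: with 10% fewer subjects in each group, the pooled formula gives 82.7% at 10% versus 40% and a minimum of 70.2%.

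**What to change.** In Section 5.1, name the test for comparing rates and attach the condition. For a pooled z or uncorrected chi-square test, suitable wording is:

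> With week-8 data on all 75 subjects and an even split, a 30-point difference has more than 80% power (two-sided 5%, normal approximation) when the lower rate is about 18% or less or about 52% or more; between these limits power may be as low as about 75%. A difference of about 32 points is detectable with 80% power at any base rate.

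If power for the chi-square test is computed exactly, the upper limit becomes about 47%, the minimum about 78% and the any-rate difference about 31 points; the lower limit stays at about 18%. If Fisher's exact test is chosen, the limits become about 13% or less and about 54% or more, the minimum about 71%, and the any-rate difference about 34 points. Only the set that matches the chosen test should appear. If the authors expect only low rates, a shorter option is to limit the claim to lower rates of about 18% or less (about 13% for Fisher) and say why.

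Keep the 10% versus 40% example; its 86% fits the pooled approximation, whereas Fisher's test gives 83.9%. The cost is one or two sentences and a slightly less favourable stated power, with no extra patients and no change to the design.

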5.2 Statistical Methods

Descriptive analyses for all variables collected at all time points will be conducted both overall and by study site. If differences are found between the study sites on outcomes of interest, then study site will be adjusted for in the analyses. For the intent-to-treat sample (i.e. those who started on drug at week 1 regardless of compliance across the 8 weeks), we will report proportions of responders and remitters and mean changes in HRSD, VAS pain score, and ARSQ from week 0 to week 8. In addition to these point estimates, we will report the corresponding 95% confidence intervals. Similar analyses will be done on the sample of completers (i.e. those who complied with drug administration across all 8 weeks based on pill counts of at least 80%).

To examine the hypothesis that baseline pain level will be predictive of response to tianeptine, we will further investigate whether any single baseline pain battery score can be used to construct subgroups of subjects showing greater response to tianeptine. Based on the distribution of a given pain battery score and preliminary exploratory bivariate modelling, we will dichotomize the pain score (low/high) and compare response/remission rates and change scores for HRSD between the groups corresponding to low and high pain battery score. We will

report effect sizes corresponding to differences in response/remission rates and differences in HRSD change scores. Exploratory analyses will employ multivariable logistic (for response/remission outcomes) and linear (for HRSD change score) regression to investigate whether combinations of baseline pain scores can be used to identify subgroups who will show greater response to tianeptine. Additional analyses will employ multivariable logistic and linear regression to investigate associations between baseline neuropsychiatric and/or MRI measures and remission/response or HRSD change score. To take advantage of the fact that HRSD and TESS are collected at each study visit (8 post-baseline measures), we will also employ linear mixed effects models to investigate the effects of each baseline pain battery score on HRSD and TESS over time.

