taper to confirm inclusion criteria are still met. Eligible subjects will then complete the remainder of the baseline evaluation, which includes the Hamilton Anxiety Rating Scale (HARS), State Trait Anxiety Inventory (STAI), Inventory of Depressive Symptomatology—Self Report (IDS-SR), Clinical Global Impressions (CGI) Severity and Improvement, Mini Mental State Examination (MMSE), physical pain tests (BPI), emotional pain tests (ARSQ, C-SSRS, Psychache scale), Drug Abuse Screen Test (DAST), and Michigan Alcohol Screen Test (MAST). Finally, for patients who are willing to participate, whole-blood samples will be drawn and used to screen for genetic polymorphisms in the genes for the mu-opioid receptor (e.g., A118→G), oxytocin receptor, vasopressin receptor 1A, and monoamine oxidase A, all of which have been shown to moderate behavioral and neural responses to rejection. Blood samples will be stored for future analysis if other potential genetic biomarkers are later identified.

Following screening and baseline measures, subjects will undergo MRI scanning, which is performed prior to Week 0. At Week 0, tianeptine medication will be initiated at 12.5 mg po tid. The first dose of tianeptine 12.5 mg is given at the Week 0 appointment under the supervision of study staff so that initial response can be observed. Subjects will be instructed not to consume any food for at least 3 hours prior to their appointment to control any food effect on tianeptine's pharmacokinetics. Orthostatic blood pressure and heart rate will be measured before tianeptine administration, subjects will be observed for a period of 1 hour.

Subjects return at Weeks 1, 2, 3, 4, 5, 6, 7, and 8 (+/- 2 days) for depression follow-up visits and complete the HRSD, CGI Severity and Improvement, IDS-SR, and Structured Pill Count Interview. At baseline, week 4 and week 8 subjects will also repeat the following tests: HARS, VAS Physical and Psychological Pain Scale. Perceived Stress Reactivity Scale (PSRS), Perceived Stress Scale Psychache Scale, UCLA Loneliness Scale, Shyness and Sociability. Reaction to Implied Rejection Measure. Hurt Feelings Questionnaire. Adult Rejection Sensitivity Questionnaire, Multidimensional Scale of Perceived Social Support, Brief Pain Inventory (BPI).. All baseline measures will be repeated at study endpoint (Week 8), including a post-treatment MRI scanning visit at NYSPI.

Revised table of procedures and timetable is shown below:

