Following screening and baseline testing, all subjects will begin tianeptine 12.5 mg three times daily (total daily dose 37.5 mg/day) for a total duration of 8 weeks of treatment. Subjects who develop side effects that prevent them from taking the full three times daily dosage will have their dosage reduced to tianeptine 12.5 mg twice daily, and those unable to tolerate at least 25 mg/day dosing will be dropped out of the study. Based on the extensive experience of clinicians in Europe, where tianeptine is approved for the treatment of depression, we expect this dosage regime to be well-tolerated. During the study, concomitant use of other antidepressants, antipsychotics, anticonvulsants, central nervous system stimulants, anti-addiction agents, and cognitive enhancers are prohibited, with the exception of small doses of benzodiazepines (≤ 2 mg lorazepam equivalents per day), which will be permitted for anxiety or insomnia.

Medication was purchased from Neuraxpharm in Germany and shipped to the NYSPI pharmacy where it is stored. Medication is shipped to the MSSM pharmacy, where it is packaged and prescribed for MSSSM patients in containers containing a 2 week supply (50 blister packed 12.5 mg pills – enough for two weeks plus an additional pills alloatted in case of a delayed visit) at the 0, 2,4, and 6 week visits and 20 blister packed pills for the final taper. Medication is shipped to the Stanford Depression Research Clinic in the same quantities and it is dispensed to patients using the same procedures as atMSSM. At each in person visit, the subject should return the bottle, and the number of remaining pills will be counted and recorded to monitor compliance.

2.7. Early discontinuation criteria and handling of emergencies.

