3.2 Exclusion Criteria

- 1) Any history of opioid-use disorder

- 2) Any history of moderate- non-opioid (except for Nicotine) substance-use disorder.
- 3) Any severity of alcohol use disorder (including mild)
- 4) Past or current psychosis, psychotic disorder (including psychotic MDD), mania, or bipolar disorder
- 5) Hamilton Rating Scale for Depression (HRSD) suicide item > 2 or Clinical Global Impressions (CGI)-Severity score of 7 at baseline
- 6) Previous or current treatment with Tianeptine
- 7) Current treatment or currently taking an opioid.
- 8) Failed depression treatment with electroconvulsive therapy.
- 9) Acute, severe, or unstable medical illness
- 10) Weight > 300 lbs, or girth size incompatible with scanner bore.
- 11) Any physical or intellectual disability adversely affecting ability to complete assessments. MMSE <26
- 12) for MSSM site - Having contraindication to MRI scanning (such as metal in body) or inability to tolerate the scanning procedures (e.g., severe obesity, claustrophobia)
- 13) Current pregnancy or currently breast feeding.
- 14) Abnormal baseline liver function tests
- 15) Currently being treated with an antidepressant medication, an antipsychotic or mood stabilizer.
 - a) If a participant is taking a protocol dis-allowed medication at the time of screening and despite medication treatment still meets the inclusion criteria of an HRSD>16, the participant may discontinue the medication under the supervision of their treating physician or the study clinician.
- 16) Positive urine toxicity at screening (except for cannabinoid)

4. Primary Study Endpoints

- 1. HRSD change from Week 0 to Week 8

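### Section 5.2 defines the intent-to-treat set by a drug start at week 1, but the protocol starts drug at Week 0; the set should be defined by the first dose

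*Combined protocol and SAP*

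**What the plan says.** Section 5.2 (Statistical Methods) introduces its main analysis set with the words "For the intent-to-treat sample (i.e. those who started on drug at week 1 regardless of compliance across the 8 weeks"). On this set it reports the proportions of responders and remitters and the mean changes in HRSD, VAS pain and ARSQ, each with a 95% confidence interval. A second, completer set is defined by pill counts.

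Section 2.5 fixes the start of treatment: "At Week 0, tianeptine medication will be initiated at 12.5 mg po tid". It adds: "The first dose of tianeptine 12.5 mg is given at the Week 0 appointment under the supervision of study staff". Follow-up comes after that: "Subjects return at Weeks 1, 2, 3, 4, 5, 6, 7, and 8 (+/- 2 days) for depression follow-up visits". The procedures table in the same section has separate columns for Week 0 and Week 1. Dispensing begins in the Week 0 column and pill counts begin in the Week 1 column.

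Section 2.6 sets treatment "for a total duration of 8 weeks of treatment" and foresees early exits, since "those unable to tolerate at least 25 mg/day dosing will be dropped out of the study". The primary endpoint in Section 4 is "HRSD change from Week 0 to Week 8". Section 5.3, whose title promises the analysis populations, describes only the kind of patient recruited.

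**The concern.** The rule that decides who is analysed names a visit at which no one starts drug. A programmer has to replace it with something, and the documents do not say what. One workable substitute is being on drug at the Week 1 visit, because pill counts and post-baseline HRSD ratings both begin there. That would remove patients who took the Week 0 dose and stopped within the first week, so membership would depend on something that happened after treatment began.

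All subjects receive tianeptine, so no control arm shares such an exclusion. Every main estimate in Section 5.2 uses this set. Section 2.1 says that 28 patients had already been entered, and Section 7.3 has the statisticians report accrued data to investigators regularly. If the wording stays open, the denominator could be settled by people who have seen results.

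**Working it through.** **1. The labels side by side.**

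| Source | What it fixes |
|---|---|
| 2.5, text | Drug starts at Week 0, first dose observed at that visit |
| 2.5, text and table | Week 1 is the first return visit, separate from Week 0 |
| 4 | Primary change runs from Week 0 to Week 8 |
| 5.2, same sentence as the definition | Changes run from week 0 to week 8, so week numbers are visit labels there |
| 5.2, last sentence | Eight post-baseline measures, which are the Week 1 to Week 8 visits |
| 5.2, the definition | Drug started at week 1 |

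Five of the six entries use one numbering, in which Week 0 is the first dose. The definition does not fit it.

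**2. Three readings of the definition.**

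- Literal, on the visit numbering: nobody qualifies. No one would implement this.
- Week 1 as the first week of treatment: every dosed patient qualifies and nothing changes.
- On drug at the Week 1 visit: patients who stopped earlier are left out.

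The text does not choose between the second and the third.

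**3. The plan's own figure.** Section 5.1 states more than 80% power for d = 0.33 with 75 subjects, two-sided 5%. A one-sample t test with df = n − 1 and noncentrality d√n = 0.33 × √75 = 2.86 gives 80.5%, so the figure reproduces. It uses all 75 subjects.

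**4. Effect of the third reading.** Let R be the responders among 75 treated and k the patients who stop before Week 1. The documents give neither, so both are assumed. If all k are non-responders, the rate moves from R/75 to R/(75 − k), a rise of Rk / [75(75 − k)]. With R = 30:

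| k left out | Response rate | Rise (points) | Power at d = 0.33, n = 75 − k |
|---|---|---|---|
| 0 | 30/75 = 40.0% | – | 80.5% |
| 2 | 30/73 = 41.1% | 1.1 | 79.4% |
| 4 | 30/71 = 42.3% | 2.3 | 78.3% |
| 6 | 30/69 = 43.5% | 3.5 | not computed |
| 8 | 30/67 = 44.8% | 4.8 | 75.9% |

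With k = 4, 22 responders give 29.3% to 31.0%, and 38 responders give 50.7% to 53.5%. Remission follows the same formula.

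The power column shows only what a smaller n does. A patient with no Week 8 HRSD has no observed change under any reading, so this loss cannot be put down to the definition alone.

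**5. Direction.** Leaving out k patients, r of them responders, raises the rate only if r/k is below R/75. If 2 are left out and 1 is a responder, the rate is 29/73 = 39.7%, below 40.0%.

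**6. Mean HRSD change.** Section 5.2 gives no rule for a missing Week 8 HRSD. Neither the size nor the sign of the effect on the primary endpoint can be worked out.

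**The case against.** A reader might infer that first-week stoppers fall outside the main set by definition, and that the error always favours the drug. The documents support neither.

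On the first, the definition turns on having started drug, not on still taking it, and it sets compliance aside for all eight weeks. Section 2.6 counts eight weeks of treatment, so week 1 could mean the first of them, which opens with the observed dose. Nothing in the protocol says that early stoppers are excluded or replaced. The exclusion needs a change of verb, from having started to being on drug.

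On the second, Section 2.7 has patients who need more intensive care complete the assessments where possible, and Section 6.1 refers to patients who stop tianeptine but stay in assessment. An early stopper can therefore have a Week 8 HRSD and can be a responder.

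The size is also open to challenge. Section 2.6 provides a dose reduction before drop-out, and the withdrawal rule in Section 2.7 that needs poor ratings at two consecutive visits can hardly operate before Week 1. A shift of 1.1 to 3.5 points is small beside the 25-point interval width allowed in Section 5.1.

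All of this stands against the stronger reading. It does not rescue the wording. Reading week 1 as a treatment week puts two numbering systems into one sentence, and Section 5.3 does not settle the matter. The inclusive intent is a reason to write the definition so that it says so.

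**Conclusion.** The definition contradicts the visit schedule and should be corrected. The contradiction itself is certain and needs no assumption. The consequence is conditional: first-week stoppers are lost only if week 1 is taken to mean being on drug at the Week 1 visit.

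On that reading, with 30 responders among 75 and all early stoppers non-responders (both assumed), the response rate is overstated by 1.1 points for 2 stoppers and 3.5 points for 6. If early stoppers respond as often as the others, the rate does not move; if more often, it falls. For the primary endpoint the effect cannot be determined. This is a modest point on size, but it concerns the rule behind every main estimate in a single-arm trial.

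**What to change.** Replace the definition in Section 5.2 with: all subjects who took at least one dose of tianeptine, starting with the observed dose at Week 0, regardless of later compliance or withdrawal. Use this set for HRSD change, response, remission, VAS and ARSQ, and keep every such subject in the response and remission denominators.

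The new wording will not by itself settle patients without a Week 8 HRSD. The plan should say beside it how such a patient is classified for response and remission, and how the missing value is handled in the mean change.

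The cost is a sentence of wording for the set, plus the statement on missing ratings. No visit or measurement changes. The reported rates may become slightly less favourable than under the narrower reading.

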The risk of non-response to tianeptine during the study period is addressed by having close clinical follow up of study subjects and stringent withdrawal criteria. These criteria are (1) participant withdraws his or her consent; (2) significant clinical worsening in the judgment of the study clinician; (3) a CGI-Improvement rating⁷ by the study clinician of 6 (worse) or 7 (much worse) for 2 consecutive visits; or (4) development of significant side effects or an adverse event grade 3 or higher. Any subject meeting any of these criteria will be withdrawn from the study and treated clinically. Furthermore, subjects may be withdrawn if they repeatedly miss scheduled appointments. If clinical worsening necessitates more intensive treatment, appropriate clinical care will be given but if possible the patient will still complete the ongoing assessments and final imaging visits.

Should a subject express suicidal ideation at any time during a study visit, the study clinician will be contacted immediately to assess the subject and to determine the appropriate course of action. Options for addressing suicidal ideation will include contacting the individual's mental health caregiver (if available), referring for urgent (same day) evaluation and treatment in an outpatient clinic, or emergency room evaluation and hospitalization. Similar practices will be used for other emergencies, including but not limited to psychosis, homicidal or violent thoughts, or an acute change in a subject's physical status.

2.8. Tianeptine taper and post-protocol treatment.

Once all study assessments are completed, subjects will be tapered off of tianeptine medication. Subjects will have their dosage reduced to 12.5 mg twice daily for two weeks, then 12.5 mg once daily for two weeks, and then tianeptine will be discontinued. Subjects will be assessed every two weeks in this post-protocol phase, with continuation of HRSD and CGI rating

scales. Appropriate clinical options will be discussed with any subject demonstrating worsening HRSD (≥ 16 on 24-item scale) or CGI (Improvement score ≥ 5 or Severity score ≥ 4 for two consecutive weeks) scores, most likely including initiation of FDA-approved antidepressant medication.

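### The primary mean HRSD change has no stated handling of patients without a week-8 score; a fully specified repeated-measures model is a cheap improvement

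*Combined protocol and SAP*

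**What the plan says.** Section 4 makes HRSD change from Week 0 to Week 8 the primary endpoint. For the intent-to-treat sample, Section 5.2 says "we will report proportions of responders and remitters and mean changes in HRSD, VAS pain score, and ARSQ from week 0 to week 8", with 95% confidence intervals. That sample is "those who started on drug at week 1 regardless of compliance across the 8 weeks". The same summaries are repeated in completers, defined by pill counts of at least 80%.

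The plan expects some patients to leave early. Section 2.6 says that "those unable to tolerate at least 25 mg/day dosing will be dropped out of the study". Section 2.7 lists withdrawal of consent, clinical worsening, a CGI-Improvement rating of "6 (worse) or 7 (much worse) for 2 consecutive visits", and significant side effects or adverse events of grade 3 or higher. It then says: "Any subject meeting any of these criteria will be withdrawn from the study and treated clinically". The same section goes on to ask that patients who need more intensive treatment finish their assessments where feasible. Section 6.1 also foresees patients who stop tianeptine but continue to be assessed.

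HRSD is collected weekly (Section 2.5), and Section 5.2 plans one longitudinal analysis of it: "we will also employ linear mixed effects models to investigate the effects of each baseline pain battery score on HRSD and TESS over time". Section 7.3 asks only that missing case-report-form data be explained. No section gives an imputation rule, a model-based estimate of the week-8 mean, or a sensitivity analysis for missing scores.

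**The concern.** The intent-to-treat definition settles who belongs to the set. It does not settle what value a member without a week-8 score contributes. A plain mean change can use only patients who have both scores.

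Several of the planned reasons for leaving are tied to doing badly. If those patients are not scored afterwards, the remaining patients look better than the treated group as a whole. In a two-arm trial some of this might cancel between arms. Here the uncontrolled mean change is itself the result, so nothing offsets it. The completer analysis selects on compliance, and the mixed model is assigned to the baseline pain predictors, so neither fills the gap.

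**Working it through.** **1. The plan's own figure.** Section 5.1 gives N = 75, d = 0.33, two-sided 5%, power above 80%. For a paired t-test the noncentrality is 0.33 × √75 = 2.86 on 74 degrees of freedom, and power is 80.5%. The figure reproduces, with a week-8 score for all 75. Power is 79.99% at n = 74 and 71.0% at n = 60.

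**2. How missing scores move the mean.** With m of 75 missing, observed mean change D_o and mean change D_m in the missing:

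error of the observed-case mean = D_o − [(75 − m)D_o + m·D_m]/75 = (m/75)(D_o − D_m).

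Take m = 15 (assumed). If the missing patients do 3 points worse, the error is 0.2 × (−3) = −0.6. At 5 points worse it is 0.2 × (−5) = −1.0. If they do the same, it is 0.

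**3. Simulation.** The documents give no attrition rate, baseline mean or variance, so every input is an assumption: n = 75; baseline HRSD 28 (SD 5); patient change −9.8 (SD 8); visit-to-visit SD 3.5; scores floored at 0, which makes the true change about −9.7; linear or square-root time course. Patients are withdrawn when HRSD is at least 5 (or 3) points above baseline at two consecutive visits. About 7% meet the 5-point trigger and up to about 15% the 3-point trigger. About 10% drop out at random as well. There were 1,200 trials per case.

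Errors in HRSD points when no later scores are obtained:

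| Trigger | Time course | Observed-case mean | Mixed model, unstructured covariance |
|---|---|---|---|
| 5 points | linear | −1.14 | −0.02 |
| 5 points | square root | −1.12 | −0.04 |
| 3 points | linear | −1.91 | −0.03 |
| 3 points | square root | −1.73 | −0.03 |

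A separate run gave the same observed-case range and a model error of at most 0.07. In these four cases the observed-case 95% interval covers the truth 59-84% of the time.

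**4. When the problem shrinks or persists.**
- All dropout random (20%): observed-case error about 0.0.
- Half of the later scores obtained: −0.5 to −0.8. All obtained, with no other treatment effect: about +0.1.
- All obtained, but other treatment lowers HRSD by 5 points (3-point trigger): both methods err, by about −0.5 to −0.7.
- Worsening visits themselves unrecorded: the model errs by −0.7 to −1.4. Adding 5 points for patients without a week-8 score brings this to −0.3 to +0.1.

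**5. The model's form matters.** In the four cases of the table, a random-intercept model with categorical visit errs by −0.5 to −1.0, about half the observed-case error. A random-slope model with linear time is near zero under the linear course but errs by +0.6 to +0.8 under the square-root course.

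**6. Response rate.** With 15 of 75 missing and 24 responders among 60 observed (assumed), the rate is 24/60 = 40.0% on observed cases and 24/75 = 32.0% with missing as non-response. If all the missing responded it would be 39/75 = 52.0%.

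**The case against.** The strongest objection is that the sizes rest on invented inputs. The protocol's triggers are clinical judgement, CGI-Improvement, side effects and consent, and nothing maps them to 3 or 5 HRSD points. The 3-point trigger partly captures measurement noise: 41% (linear) and 25% (square root) of those it removes would have been below baseline at week 8. The model's near-zero error follows from tying withdrawal to recorded HRSD, which is missing at random by construction. Section 2.6 also expects the drug to be well tolerated. All of this stands. The figures illustrate the problem and do not forecast it.

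The error would also not overturn a finding that HRSD fell. The assumed change is 9.7/9.2 = 1.05 standard deviations, against the 0.33 that the plan is sized to detect. That stands too: what suffers is the size of the estimate and its interval.

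Some stronger readings are tempting, and the documents do not support them:
- A reader might infer that the power statement is wrong. It reproduces; it simply assumes complete week-8 data.
- A reader might infer that the response and remission rates have no denominator. Read plainly, the intent-to-treat definition supplies one: all who started. What is missing is how a starter without a week-8 score is classified. The remission endpoint in Section 4.1 refers to a final score, which could mean the last available one, but the term is undefined and applies only to remission.
- A reader might infer that patients lost in the first week are excluded, because the sample is defined from week 1. Section 2.5 says "The first dose of tianeptine 12.5 mg is given at the Week 0 appointment under the supervision of study staff", so this is probably a labelling slip.
- A reader might infer from Section 7.3 that the rule will be chosen with results in view. The reports to investigators described there serve data checking.

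**Conclusion.** The gap is real, and closing it is a cheap improvement. Sections 2.6 and 2.7 make outcome-related loss of week-8 scores plausible, and Section 5.2 offers only a plain mean change for the primary result.

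If worsened patients leave and are not scored again, that mean is too favourable: by about 1.1 to 1.9 points in the assumed cases, or 11-20% of a 9.7-point improvement (1.1/9.7 and 1.9/9.7). If dropout is unrelated to outcome, or all later scores are obtained without other treatment, there is essentially no error. The documents do not show which of these will occur, so they do not support saying that the result will be biased.

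The case for the model does not depend on the exact sizes. It uses weekly data already collected, and it loses nothing in expectation when dropout is random. Its advantage does depend on the covariance structure and time coding being stated, and on the worsening being recorded before the patient leaves.

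**What to change.** 1. In Section 5.2, estimate the week-8 HRSD change and its 95% confidence interval from a repeated-measures mixed model on all HRSD scores from Week 0 to Week 8 of all dosed patients, with visit as a category and unstructured covariance. State the missing-at-random assumption. Add a sensitivity analysis that makes patients without a week-8 score worse, for example by 3 and 5 points; with 15 of 75 missing this moves the mean by 0.6 and 1.0.
2. Keep all dosed patients in the denominator for response and remission. Report the rate with missing counted as non-response beside the observed-case rate.
3. State whether HRSD scores obtained after other antidepressant treatment count. Reconcile the two statements in Section 2.7, one withdrawing patients from the study and the other asking that worsened patients complete their assessments.

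The cost is wording and one extra model, with no new visits or patients. The downsides are reliance on missing at random (bias remains if worsening visits go unrecorded) and a possibly less favourable estimate. Counting missing as non-response is conservative and may understate the true rate. Across 20 simulated cases it was closer to the truth than the observed-case rate in only 4, which is why both should be shown.
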